The International Consultation on Incontinence Questionnaire Short-Form (ICIQ-SF) is one of a series of International Consultation on Incontinence questionnaires that have been meticulously developed and tested.²⁴⁻²⁷ The ICI questionnaires are becoming the outcome measures of choice in incontinence clinical trials internationally,²⁸⁻²⁹ allowing comparability between studies. The ICIQ-SF is a brief (4 items), reliable (Cronbach's alpha = 0.95), questionnaire that quantifies both symptom burden and impact of incontinence and has been validated in men and women. We have piloted the ICIQ-SF and patients have found it very quick and easy to complete. The ICIQ-SF correlated well with urodynamic outcomes in men and women,²⁵ and 24-hour pad tests, the International Prostate Symptom Score (IPSS), and Postoperative Patient Global Impression of Improvement (PGI-I) Score in men undergoing surgical treatment for post-prostatectomy incontinence.²⁶

The primary patient outcome is time to continence as measured by the ICIQ-SF. The ICIQ-SF is designed, in part, to screen for incontinence and is completely appropriate to determine if a person no longer has incontinence. We used time to continence in our previous clinical trial of preoperative training to prevent post-prostatectomy incontinence.⁴ Time to continence also has face validity since it is extremely important to the patient who wants to regain continence as soon as possible after his surgery. The ICIQ-SF will be completed weekly for 6 months post-operatively via the telehealth program. Each telehealth screen related to the ICIQ-SF will be prefaced with "During the last week" to make the timeframe clear. When a participant reports no incontinence on the ICIQ-SF (an answer of "never" to "In the last week, how often did you leak urine?") for 3 weeks in a row, we will consider him continent. We successfully used the definition of no reported leakage for 3 weeks based on weekly bladder diaries in our prior study of preoperative training to prevent post-prostatectomy incontinence.⁴ Although it is likely that participants who achieve this endpoint may still have occasional leakage, such as with heavy lifting or a good laugh, experience has shown that these men do not consider themselves incontinent. The total score of the ICIQ-SF will also be used to evaluate patient outcomes. The ICIQ-SF score has shown sensitivity to change with treatment in men with post-prostatectomy incontinence.²⁶ We will also compare continence rates at 9 and 12 months.

Secondary Outcome Measures

Expanded Prostate Cancer Index Urinary Incontinence Subscale (EPIC-UI): This measure, validated as a stand-alone assessment, consists of 4 questions from the EPIC,³⁰ a health-related quality of life (HRQOL) assessment tool. The EPIC was developed based on advice from an expert panel and prostate cancer survivors, expanding the 20-item University of California-Los Angeles Prostate Cancer Index (UCLA-PCI) to 50 items that quantify symptoms and bother associated with urinary, sexual, bowel, and hormonal domains. Summary and subscale scores were derived by content and factor analyses. Reliability and validity of the total and subscales were assessed by test-retest correlation, Cronbach's alpha coefficient, inter-scale correlation, and EPIC correlation with other validated instruments. Test-retest reliability and internal consistency were high for the EPIC-UI with ($r = 0.87$ and Cronbach's alpha = 0.89). In addition to the subscale score, the EPIC-UI question on pad use will be used as descriptive data. Although more valid measures are now recommended, pad use is an outcome that has been used in many post-prostatectomy incontinence trials and is important for comparability across trials.

Incontinence Impact Questionnaire - Short Form (IIQ-SF) This measure, validated in men with post-prostatectomy incontinence, measures the impact of incontinence on regular activities.³¹ It is a condition-

specific quality of life measure that has been widely used in incontinence clinical trials. It is sensitive to pre-post changes after treatment. See **Figure 1**.

Figure 1 Incontinence Impact Questionnaire – Short Form				
Has urine leakage affected your:	Not at all	Slightly	Moderately	Greatly
1. Ability to do household chores (cooking, housecleaning, laundry)?				
2. Physical recreation such as walking, swimming, or other exercise?				
3. Entertainment activities (movies, concerts, etc)?				
4. Ability to travel by car or bus more than 30 minutes from home?				
5. Participation in social activities outside your house?				
6. Emotional health (nervousness, depression, etc)?				
7. Feeling frustrated?				

IPSS Quality of Life Question.³² Frequently administered with the AUA Symptom Index, this validated quality of life measure has been shown to be sensitive to change after treatment in clinical trials including our own work. It is shown in **Figure 2**.

Figure 2 - IPSS Quality of Life Question: If you were to spend the rest of your life with your urinary problem the way it is now, how would you feel about that? ↑
 Delighted, Pleased, Mostly satisfied, Mixed (about equally satisfied and dissatisfied), Mostly dissatisfied, Unhappy, Terrible

Other Quality of Life Questions: We have supplemented the validated questionnaires with additional quality of life questions in much of our past research.^{4,18-21} These additional data points provide additional information of the impact of incontinence. We plan to ask the participants the following questions each month 1-6 months post-operatively and again at 9 & 12 months post-operatively:

- How disturbing is the urine leakage problem to you? (not at all, somewhat, or extremely disturbing)
- How much does leakage of urine restrict your activities? (not at all, some of the time, most of the time, all of the time).
- Have you been able to return to work since your surgery? (yes, no, retired or disabled)
- Have you been able to resume your usual activities since your surgery? (yes, no)

Exercise Adherence Questionnaire: We will measure adherence to exercises monthly, more frequently as the exercise routine is being established, with a brief questionnaire used in our NIH-funded incontinence research since 1989, including our trial of pelvic floor rehabilitation for post-prostatectomy incontinence,⁴

and also, the VA Rehab R&D-funded study of pelvic floor rehabilitation for overactive bladder in men.¹⁸ The questionnaire is shown in **Figure 3**. If the participant answers “No” to “Are you doing the pelvic floor muscle exercises?” the next two questions would not appear. Instead, the participant will see screens designed to help him surmount barriers **to adherence**. Participants in the experimental group will also get monthly measures of bladder control strategy adherence – i.e., using the pelvic floor muscles to prevent stress and urge leakage.

Figure 3 - Exercise Adherence Questionnaire

Are you doing the pelvic floor muscle exercises? (Yes or No)

If yes: How many days did you do the exercises in the last week? _____

How many exercises do you do in a typical day? _____

Patient Satisfaction Question (PSQ), Estimated Percent Improvement (EPI), and Global Perception of Improvement (GPI): As in the most recent publication by the International Consultation on Incontinence conducted in 2009, the International Scientific Committee recommended that urinary incontinence clinical trials include one or more high quality, validated instruments representing the viewpoint of the patient.³³ Subjective patient assessments have been deemed so important that in one trial of pelvic floor muscle rehabilitation in the NIH Pelvic Floor Disorders Network, it was the consensus of the expert panel to use a single global patient rating of improvement as the primary outcome measure.^{34,35} We propose three patient perception assessments developed by the investigators to capture patient perceptions of improvement and satisfaction (**Figure 4**).³³ The Estimated Percent Improvement (EPI) and Global Perception of Improvement (GPI) are two simple questions that allow the patient to estimate his improvement after treatment; response on one is continuous and the other categorical. The Patient Satisfaction Question, on the other hand, captures patient satisfaction with treatment on a visual analog scale from 0 to 100%. This outcome is very important since there can be different levels of satisfaction with similar degrees of improvement and vice versa.^{20,21} We used these measures in our Rehab R&D-funded project, “Behavioral Treatment for Overactive Bladder in Men,” (Merit Award B02-2489R, PI - [name]).¹⁸

Figure 4 – Global Patient Perception Assessments

PSQ: How satisfied are you with your progress in controlling your bladder?
Completely // Somewhat // Not at All

GPI: Overall, do you feel that you are: Much better // Better // About the same // Worse // Much worse

EPI: Estimate how much better you are on a scale from:
0% (no better) to 100% (completely better).
_____ %

During validation of these assessment questions, convergent validity was established by examining the relationship between each measure and reduction of incontinence episodes (based on bladder diary), change on the Incontinence Impact Questionnaire (IIQ), a validated incontinence-specific quality of life tool, and patients’ desire for another treatment. Discriminant validity was tested by examining the relationship of the global ratings to five measures not expected to be related to outcome (age, race, BMI, education level, and change in perceived pain). The PSQ, EPI and GPI demonstrated acceptable convergent and discriminant validity for measuring outcomes in studies of treatment for urinary incontinence.³³ The schedule of data collection is shown in **Table 4** (above).

Qualitative Assessment

At 6 months postoperatively, after completing the core curriculum, 30 participants in the active treatment group will complete an in-person or telephone assessment of their experience using a semi-structured interview guide developed by [name] and our research team (**Table 5**). The telephone or in-person interview will be conducted by [name] in Atlanta to evaluate any suggestions participants have and as well as gather any suggestions for changes to the telehealth program. The session is recorded, with the participant’s permission. To optimize patient feedback from those who can best express their critique and

suggestions on paper, this option will be available to participants as well. Based on participant input, modifications will be made to the telehealth curriculum.

Table 5 - Semi-Structured Interview Guide

I. Technology Issues

- a. If you used a Health Buddy, can you tell me about your experience with setting up the telehealth device in your home?
 - i. How easy or difficult was the initial set-up?
 - ii. Where did you place the telehealth device in your house?
 - iii. Was this location someplace convenient to your daily routine?
 - iv. Did anyone notice the telehealth device and ask questions about it? How was it answering their questions?
- b. Can you tell me about how it was to use the telehealth program?
 - i. What time of day did you usually do your telehealth sessions?
 - ii. How convenient or challenging was it to find the time each day to do the telehealth session?
 - iii. Did you usually do this alone or was someone with you when you used the telehealth program? If someone helped: How did that work for you?
 - iv. If you used a Health Buddy or loaner tablet, did you experience any problems with the telehealth equipment?

II. Module Content

- a. What did you think about the information you received through the telehealth program?
 - i. Was the print size easy or hard to read?
 - ii. Was the information easy or challenging to understand?
 - iii. Did the information flow in an order that made sense or was it confusing?
 - iv. Overall, did the program move at the right speed? Or was it too slow or too fast?
 - v. Was the information helpful?
 - vi. What in particular was most helpful?
 - vii. What was the least helpful?
 - viii. What did you think about the patient stories?
 - ix. What did you think about the fun facts?
- b. Can you tell me about what it was like for you to do the pelvic muscle exercises?
 - i. How difficult was it for you to locate your pelvic muscles?
 - ii. How easy or challenging is it for you to practice the exercises each day?
 - iii. What reminders do you use to help you to remember to do your exercises?

III. Overall Evaluation

- a. Overall, did you like the telehealth Program?
- b. Did it meet the expectations you had when you signed up for the program?
- c. Does it make sense to you to learn this information using the telehealth program or would you prefer learning it another way? (like in the clinic or from a booklet)

IV. Suggestions

- a. What suggestions do you have for improving the telehealth Program?
- b. Is there anything else you would like to share about your experience with this equipment or information that you think we ought to know that would be helpful for other patients?
- c. Would you recommend this to other men who are planning to have prostatectomy surgery?

We have been successfully using this Interview Guide during the pilot study. We will continue to collect qualitative data in the RCT. A sample size of 30 will ensure that important characteristics of participants' experiences are not overlooked and that there is sufficient variation in participants' perceptions and experiences to identify most, if not all, of the relevant themes.

As shown in **Table 6**, an N of 30 reduces the probability of missing a perspective with a 10%-incidence to less than 5%. This translates into 95% confidence of identifying any qualitative insight that will contribute to our characterization of participants experiences with the intervention.³⁶ This data is assisting us with improvements in the telehealth program now as a result of being used in the pilot study and will be quite useful in description of the telehealth modules development and in dissemination.

Table 6. The probability of missing a population subgroup in a random sample

Population Incidence	Number of Respondents							
	10	20	30	40	50	60	100	200
.50	.001	<.001	<.001	<.001	<.001	<.001	<.001	<.001
.33	.018	<.001	<.001	<.001	<.001	<.001	<.001	<.001
.25	.056	.003	<.001	<.001	<.001	<.001	<.001	<.001
.20	.107	.012	.001	<.001	<.001	<.001	<.001	<.001
.10	.349*	.122	.042*	.015	.005*	.002	<.001	<.001
.05	.599	.358	.215	.129	.077	.046	.006*	<.001
.01	.904	.818	.740	.669	.605	.547	.366	.134

Data Management

The telehealth programs use encrypted data with a proprietary 128-bit encryption technology that has been approved by VA security audits and is downloaded nightly from the Health Buddy to the VA Austin Automation Center or stored on the secure vendor website. Bosch also maintains a duplicate failover facility in the VA facility at Hines IL. Both databases are synced daily so the chance of data loss is extremely low. The transfer of data is via a toll-free call at no expense to the participant. If the call is interrupted, the Health Buddy recalls the center and retransmits all of the data. Data downloads to our research site will be via a shared-access VA server, other than the programmed alerts based on patients' replies to the Health Buddy dialogues, which will be transmitted the day received to prompt a call to the patient from a nurse practitioner at our center. If a participant has not completed the telehealth outcome measures for 1 week, they will be administered in-person or by telephone and barriers will be problem solved to increase adherence. All adherence and nurse practitioner time will be tracked. We will differentiate contact necessary for the participant to master the content of the rehabilitation program from contact necessary to collect study outcome measures on time. This will be important to dissemination planning.

For the data collected at the Birmingham and Atlanta VAMCs by in-person or telephone interviews and CPRS audit, the research documents will be scanned and uploaded to a SharePoint site behind a VA firewall. The paper copies will be kept in a secure and locked location in the Geriatric Research, Education, and Clinical Center (GRECC). The data will be entered into a SPSS database and stored on a secure VA server by the data manager. Information abstracted from the VA Computerized Patient Record System (CPRS) will be entered onto paper forms that will then be entered into the same SPSS database. A back-up SPSS database will be stored on a different VA server in a different location. The databases will be deidentified. The name and study number key will be stored in separate files on each of the servers. To ensure the accuracy of the data, a percentage of the data entered from paper records will be subject to dual entry with the percentage adjusted

up or down depending on the error rate detected. Manual inspection of the forms will be done to resolve differences in the dually entered data. The principal investigator and statistician will meet with the database manager to review accrual, data entry, and examine the database for outliers or data base entry errors monthly.

Data Analysis

Preliminary Analyses

Although subjects will be stratified and randomized, the equivalency of the two groups will be evaluated on selected variables that might influence treatment outcome: study site, age, nerve sparing surgery, body mass index. The chi square statistic will be used for the categorical variables and the two-sample t test for continuous variables. Normality will be carefully assessed for continuous outcomes and if the assumption is violated, non-parametric methods will be used.

Outcome Variables Analysis

Primary outcome analysis: duration of incontinence (time to achieve continence after surgery). Participants will be considered continent if they answer that they leak urine “never” on the ICIQ-SF for 3 weeks in a row. Please see Methodology section for complete explanation of this measure. Baseline time for this measure will be the day of surgery. Median time until continence and its 95% confidence interval will be calculated per group. The duration of incontinence will be examined using the Kaplan-Meier procedure, in which all protocol eligible participants are analyzed. Men who did not have a prostatectomy – either due to positive lymph nodes during surgery or because they changed their mind and selected another treatment after randomization but before surgery will not be included in the analysis. All other men randomized will be included. The duration of incontinence will be compared between the 2 groups using the log rank test. We will also compare continence rates at 9 and 12 months.

Secondary outcome analyses (severity of incontinence, impact on quality of life, and patient reported evaluations of improvement and satisfaction with treatment) will be measured by:

1. ICIQ-SF total score
2. EPIC-UI total score
3. Pad use from the EPIC-UI
4. Patient estimation of improvement measured by the GPI and EPI
5. Patient satisfaction as measured by the PSQ
6. IIQ – total and subscale scores
7. IPSS Quality of Life Question (IPSS QoL)
8. Questions on activity restriction, amount of disturbance caused by incontinence
9. Return to work or normal activities after surgery.

Our hypothesis for the secondary outcomes is that total ICIQ-SF, EPIC-UI total Score, Pad use, GPI, EPI, PSQ, IIQ, IPSS QoL, return to work or normal activity, and amount of disturbance caused by incontinence will be better in the pelvic floor muscle rehabilitation group.

Initially, descriptive analyses will be conducted to examine distributions of the frequency of symptoms and possible covariates. Extreme values will be checked for accuracy and recoded as indicated. Transformations may be employed to correct for skewness or heterogeneity as needed.

The ICIQ-SF total score and the EPIC-UI total score will be analyzed using multiple regression analysis to regress the 6 and 12-month scores on treatment group, while controlling for baseline score (first score after catheter removal post-operatively). Pad use will be dichotomized into no pad use and any pad use. Pad use will also be analyzed descriptively as no pads, 1 pad, or 2 or more pads. The chi square statistic and the t test for independent samples will be used. Both measures are necessary for comparison with earlier studies. Multiple regression will be used for the GPI, EPI, and PSQ at 6 and 12 months. There is no baseline for these measures as they are the patients’ evaluations of their improvement and treatment satisfaction. For the IPSS QoL question, questions on activity restriction, disturbance, and return to work or normal activity, the chi square statistic and the t test for independent samples will be used.

Qualitative Analysis

To ensure analytic rigor, the following procedures will be followed: (1) data immersion (reading/listening and re-reading/listening to the text); (2) thematic identification and articulation (discovering, naming, defining codes/variables); (3) data categorization (developing a coding scheme); (4) pattern articulation (identifying connections within and between codes); (5) data interpretation (recognizing how the patterns transcend individual experiences and reflect larger social processes). As an analytical process, content analysis involves sorting and making sense of written and narrative data. The goal is not to generalize across a population, but rather to provide understanding and explanation from the respondent's perspective.

DISSEMINATION PLAN

Before dissemination, data from the qualitative analysis of the semi-structured interviews with participants in the active treatment group as well as any themes that arose in our debriefing meetings regarding the nurse practitioner "rescue calls" will be used for final modifications to the program.

We will be using a theoretical framework to guide dissemination, the Promoting Action on Research Implementation in Health Services (PARIHS) framework.³⁷¹⁴⁰ The PARIHS model is ideal for dissemination of a telehealth-administered program because it focuses on systems of care rather than individual provider or patient response to proposed change. The PARIHS framework proposes that successful implementation of evidence in practice is dependent on the inter-relationship of three key elements: the nature of the evidence, the quality of the context, and expert facilitation. For successful implementation, evidence needs to be robust, the context receptive to change, and appropriate facilitation provided. This RRD-funded grant will provide the evidence and the successful context. The investigators will be actively involved in the dissemination process to facilitate implementation.

The dissemination will be through the VA Care Coordination/Home Telehealth (CCHT) program. As per the PARIHS framework, to establish the nature of the evidence, teaching sessions via teleconference will be done for the CCHT staff to describe the burden on Veterans as a result of a diagnosis of prostate cancer, the excellent prognosis, but the resulting incontinence in men electing surgical treatment. Further, evidence of the effectiveness of perioperative pelvic floor rehabilitation and specifically that the telehealth program is effective to assist Veterans undergoing prostate cancer surgery to recover continence sooner and that it also improves their quality of life will be presented. We will include patient testimonials from our patient debriefings and qualitative analysis. We will provide similar educational sessions for Urology Clinic nurses, nurse practitioners, and physicians assistants. Their assistance will be crucial to help identify Veterans about to have prostate cancer surgery so they can participate in the preoperative rehabilitation model. CCHT teams can also monitor the surgery schedules so that any patients missed pre-operatively can be enrolled immediately after surgery.

Per the PARIHS framework, to establish the quality of the context and receptivity to this new program, input regarding any anticipated difficulties in implementation will be solicited after each teleconference so that they can be addressed.

To provide expert facilitation during implementation, we will provide telephone support as CCHTs start using this new module and continue as long as necessary. So far in the pilot study, patient telephone support beyond a phone call to encourage a few Veterans to start the program has not been necessary. If this proves to be so in the RCT, then the CCHT personnel would not need additional expertise to monitor patients enrolled in the program. The training as described above will be sufficient for them to implement the program.

Unlike many treatment protocols developed and proven effective by research teams that average 10 years to become common practice, the delivery system for this intervention has a strong existing infrastructure, the CCHT program. As mentioned earlier in the grant proposal, there has been a 30-fold growth in the CCHT program from 10,000 Veterans served in FY2006 to 300,000 in FY2010. There are 3 major reasons for this growth: 1) the CCHT program is mandated in every VA, 2) funding to each VAMC is based on the number of Veterans enrolled, so there is motivation to enroll Veterans into the program, and 3) the Veterans really like these simple home messaging devices and take pride in the improvements in their knowledge and health. This completely fits into the Health Belief Model, which is our theoretical framework for the study. The home

messaging units cue the Veterans to action, provide the information they need for an action plan, and help them achieve benefits that are clinically meaningful.

Done optimally, dissemination will take the better part of a year and will be performed as part of the GRECC mission of disseminating successful clinical dissemination projects. GRECC investigators will also revise the content of the program as necessary in the future as guided by new science and practice.

To assist in dissemination, we will also present the results of the clinical trial at the American Urological Association annual meeting and publish the manuscripts in prominent medical journals such as JAMA or the Journal of Urology, with an article describing the development of the program in the Federal Practitioner.

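### Thirty interviews carry under 5% risk of missing one view held by 10% of men sampled at random, not 95% confidence of finding any insight, and no selection rule is stated

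*Combined protocol and SAP*

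**What the plan says.** The Qualitative Assessment section gives the timing and source of the interviews: at 6 months after surgery, "after completing the core curriculum, 30 participants in the active treatment group will complete an in-person or telephone assessment". The section does not say how the 30 are chosen, sets no criterion for having completed the curriculum, and does not mention men who stopped using the programme.

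It says that 30 gives enough variation "to identify most, if not all, of the relevant themes". The support is Table 6, titled "The probability of missing a population subgroup in a random sample". From it the text concludes that "an N of 30 reduces the probability of missing a perspective with a 10%-incidence to less than 5" percent. The next sentence goes further: "This translates into 95% confidence of identifying any qualitative insight that will contribute to our characterization of participants experiences with the intervention".

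The results are put to use. The same section says the curriculum will be modified on participants' input. The Dissemination Plan bases the final modifications on "data from the qualitative analysis of the semi-structured interviews with participants in the active treatment group", together with themes from staff debriefings about nurse practitioner calls.

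**The concern.** The last step of the argument drops two conditions. Table 6 concerns one view at a time, at a stated incidence, in a random sample. The concluding sentence speaks of any insight, at no stated incidence, from 30 men whose selection is not described. The sample size is therefore justified by a property that the design does not have.

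The clause about the curriculum adds a doubt about who is interviewed. If it is applied as an entry condition, views concentrated among men who gave up the programme would be heard less often than Table 6 implies. Those men can best say why it did not work for them, and the interviews help to shape the version that goes into VA-wide use.

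**Working it through.** **Inputs.** Number interviewed, 30, active arm only (Qualitative Assessment). Target incidence 10% (text introducing Table 6). Telehealth arm of 78 (Sample size). The share of active-arm men who stop is not given, so 5% to 30% is assumed below.

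**Step 1: reproduce the plan's figure.** The probability that n random respondents all lack a view of incidence p is (1 − p)^n. With n = 30 and p = .10, .9^30 = .0424, against .042 in Table 6. The other cells of the table also reproduce, to about .001. The arithmetic of the table is right.

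**Step 2: what 95% covers.** Setting (1 − p)^30 = .05 gives p = 1 − .05^(1/30) = .095. So 30 random interviews give 95% probability of hearing at least once a single view held by about 9.5% or more of the group. For rarer views, the table's own column for 30 shows:

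- 5% incidence: .95^30 = .215
- 1% incidence: .99^30 = .740

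**Step 3: allow for a finite arm.** Drawing 30 of 78 without replacement, the probability of missing a view held by k men is C(78 − k, 30)/C(78, 30). This is .016 for k = 8 (10.3% of the arm), .136 for k = 4 (5.1%) and .615 for k = 1 (1.3%). The 10% figure improves, but the claim about any insight still fails.

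**Step 4: if only completers were interviewed.** Let s be the share of the arm that stops and f the share of a view's holders who are among those men. Both are assumptions. A view held by 10% of the whole arm then has incidence .10 × (1 − f)/(1 − s) among completers. With s = .10 and f = .50 this is .10 × .50/.90 = .0556, and (1 − .0556)^30 = .180. Over the assumed range, the probability of missing the view is:

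| Share stopping (s) | f = 0 | f = 25% | f = 50% |
|---|---|---|---|
| 5% | .036 | .085 | .198 |
| 10% | .029 | .074 | .180 |
| 20% | .018 | .052 | .144 |
| 30% | .010 | .033 | .108 |

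The probability rises above .042 only when f exceeds s, that is, when men who stopped are over-represented among the view's holders. For a view unrelated to stopping (f = s), the 10% figure is unchanged.

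**The case against.** **The claim is softer in context.** The 10% condition stands in the sentence just before, Table 6 prints the weaker figures openly, and the Qualitative Analysis section says the aim is not to generalise to a population. This is fair as to intent. But the concluding sentence carries no such limit, and it is the one that justifies the sample size.

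**The curriculum clause may only describe timing.** A reader might infer that men who stopped are excluded and so certain to be missed, and that this is why the 95% fails. The documents do not establish that. No completion criterion is written. The daily programme ends 2 months after surgery and the interview is at 6 months, so the clause fits as a description of sequence. The Follow-Up section uses the same construction to introduce weekly outcome assessments that apply to participants generally, with telephone prompts for men who miss one. Step 2 also shows that the claim fails in a random sample of the whole arm, so exclusion is not the cause. This part of the objection stands. What remains is that the wording is open and the selection rule is absent.

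**Non-use is followed elsewhere.** A reader might infer that a null result could not be traced to men abandoning the programme. That too is unsupported. The Intervention section asks men who have not resumed exercises for the reason, and a week without use triggers an alert and a call. Treatment Fidelity provides weekly review of contacts with men not doing their sessions. Programme use and adherence are recorded, and call debriefings feed the final modifications. These sources give partial coverage. They are not recorded participant interviews, and the interview guide in Table 5 has no question on why a man stopped.

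**Conclusion.** The concern holds in limited form. Table 6 supports a probability below 5% of missing one given view held by about 10% or more of the group sampled, if the 30 are a random sample of that group. It does not support 95% confidence for any insight: the probability of a miss is .215 at 5% incidence and .740 at 1%. These figures come from the plan's own table and need no outside assumption.

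The point about men who stopped is conditional. It applies only if the curriculum clause is used as an entry condition, and only to views concentrated among those men. The .18 rests on two assumed inputs, 10% stopping and half of the view's holders among them. With half of the holders stopping, the assumed 5% to 30% range of stopping gives .198 to .108.

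The matter is minor. It touches the qualitative component and the programme changes drawn from it, and leaves the time-to-continence analysis unaffected.

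**What to change.** 1. Replace the 95% sentence after Table 6 with: under 5% probability of missing any single perspective held by at least 10% of the group sampled from, assuming random sampling.
2. Reword the Qualitative Assessment section so that the 30 are drawn at random at 6 months from all active-arm men who had surgery, whether or not they finished the curriculum. Keeping the 6-month timing largely avoids extra contact in one arm only while the weekly primary outcome is being collected.
3. Add one question to the Table 5 guide, for men who stopped, on why they stopped.

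If the team prefers to reserve some places for men who stopped, Table 6 should not be applied to the combined 30, because a quota is not a simple random sample. Reserving 6 to 8 places, for example, leaves 24 to 22 completers. A view held by 10% of completers and by no one who stopped would then be missed with probability .9^24 = .080 to .9^22 = .098, above the stated 5%.

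The cost is wording and one question, with the same number of interviews. Men who stopped are harder to reach, and slightly fewer completers are interviewed: at an assumed 10% stopping, about 30 × .10 = 3 of the 30 would be men who stopped.
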